5.3.2 Caffeine, Alcohol, and Tobacco

No restrictions are applicable.

5.3.3 Activity

Participants will abstain from strenuous exercise for 4 hours before each blood collection for clinical laboratory tests. Participants may participate in light recreational activities (e.g., watching television or reading).

5.4 Screen Failures

Individuals in Part A who do not meet the hematological and/or renal criteria for participation in this study (screen failure) may be rescreened once. Rescreened participants will be assigned a new participant number. Rescreening does not apply to participants intended for Part B.

6 Study Intervention(s)

Study intervention is any investigational intervention(s), marketed product(s), placebo, or medical device(s) intended to be administered to a study participant per the study protocol.

6.1 Study Intervention(s) Administration

Study Intervention Name:	M3258 PiCs
Dose Formulation:	Powder in Capsules (PiCs)
Unit Dose Strength(s)/ Dosage Level(s):	1 mg, 5 mg, 30 mg
Route of Administration:	Oral
Dosing Instructions:	See Section 6.6 (Dose Selection and Modification).
Supplier/Manufacturer:	The Sponsor will supply the study intervention.
Packaging and Labeling	PiCs will be supplied in CCI [REDACTED] packs. Each CCI [REDACTED] pack will be packaged and labeled per all applicable regulatory requirements and Good Manufacturing Practice Guidelines.

In addition, commercially available dexamethasone to be given at the regimen proposed in Section 4.1 for oral administration will be provided locally by the site as per local available dosage.

6.1.1 Medical Device(s) Use

Not applicable.

6.2 Study Intervention(s) Preparation, Handling, Storage, and Accountability

The Investigator, institution, or the head of the medical institution (where applicable) is responsible for study intervention accountability, reconciliation, and record maintenance (i.e., receipt, reconciliation, and final disposition records).

- Upon receipt of the study intervention(s), the Investigator or designee must confirm appropriate temperature conditions have been maintained during transit and any

discrepancies are reported and resolved before use. Also, the responsible person will check for accurate delivery and acknowledge receipt by signing or initialing and dating the appropriate document and returning it to the location specified. A copy will be archived for the Investigator Site File.

- Only participants enrolled in the study may receive study intervention(s) and only authorized site staff may supply it. All study intervention(s) must be stored in a secure, environmentally-controlled, and monitored (manual or automated) area, in accordance with the labeled storage conditions, and with access limited to the Investigator and authorized site staff.
- Dispensing will be recorded on the appropriate accountability forms so that accurate records will be available for verification at each monitoring visit.
- Study intervention(s) accountability records at the study site will include the following:
 - Confirmation of receipt, in good condition and in the defined temperature range.
 - The inventory provided for the clinical study and prepared at the site.
 - The dose(s) each participant used during the study.
 - The disposition (including return, if applicable) of any unused study intervention(s).
 - Dates, quantities, batch numbers, kit numbers, expiry dates, and the participant numbers.
- The Investigator site will maintain records, which adequately documents that participants were provided the doses specified in this protocol, and all study intervention(s) provided were fully reconciled.
- Unused study intervention(s) must not be discarded or used for any purpose other than the present study. No study intervention that is dispensed to a participant may be re-dispensed to a different participant.
- A Study Monitor will periodically collect the study intervention(s) accountability forms.
- Further guidance and information for the final disposition of unused study intervention(s) are provided in the Operations Manual.

6.3 Measures to Minimize Bias: Study Intervention Assignment and Blinding

6.3.1 Study Intervention Assignment

Not applicable.

6.3.2 Blinding

Not applicable.

6.3.3 Emergency Unblinding

Not applicable.

6.4 Study Intervention Compliance

In this study, participants will receive study intervention at the investigational site on visit days. Trained medical staff will monitor and/or perform the on-site study intervention administration. Participants will be instructed by the Investigator/designee regarding off-site self-administration of M3258, and compliance checks performed at all study visits. The information of each study intervention administration (date and dose of study intervention) will be recorded in the participant notes and electronic Case Report Form (eCRF). On days preceding PK, sampling time of drug intake will also be recorded. The Investigator will ensure that the information entered into the eCRF regarding drug administration is accurate for each participant. Any reason for noncompliance should be documented. In the situation where participants discontinue study intervention for more than 5 days per cycle, or if ≥ 6 consecutive planned doses of M3258 are missed for reasons other than toxicity unless, upon consultation with the Sponsor and the review of safety and efficacy, continuation is agreed upon (Sections 7.1 and 8.4).

6.5 Concomitant Therapy

Record in the eCRF all concomitant therapies (e.g., medicines or nondrug interventions) used from the time the participant signs the informed consent until completion of the study, including any changes. For prescription and over-the-counter medicines, vaccines, vitamins, and herbal supplements, record the name, reason for use, dates administered, and dosing information.

Contact the Medical Monitor for any questions on concomitant or prior therapy.

Participants must abstain from taking prescription or nonprescription drugs (including vitamins and dietary or herbal supplements) within 7 days (also for potential enzyme inducers) or 5 half-lives (whichever is longer) before the start of study intervention until completion of the study intervention administration, unless, in the opinion of the Investigator and Sponsor, the medication will not interfere with the study (see Section 6.5.2 for permitted medicines; Section 6.5.3 for prohibited medicines).

Antiviral prophylaxis for Herpes zoster (e.g., acyclovir, valacyclovir) is permitted.

Antiemetic and antidiarrheal medications may be required and will be administered according to institutional guidelines. A minimal oral hydration of 2 liters/day is recommended for participants to prevent dehydration and hyperviscosity.

Paracetamol/acetaminophen, at doses of ≤ 2 grams/24 hours, is permitted for use any time during the study. Other concomitant medication may be considered on a case-by-case basis by the Investigator in consultation with the Medical Monitor if required.

6.5.1 Rescue Medicine

Not applicable.

6.5.2 Permitted Medicines

Any medicines that are considered necessary to protect the participant's welfare in emergencies may be given at the Investigator's discretion, regardless if it results in a protocol deviation. All permitted drugs need to be entered in the eCRF.

Standard supportive care for MM such as transfusions, intravenous Ig, pneumonia prophylaxis, flu and pneumonia vaccines are allowed during treatment. However, treatment with transfusions or growth factors (e.g., granulocyte-colony stimulating factor [G-CSF], erythropoietin) is not permitted during the DLT period.

Bisphosphonates should be considered in all participants with myeloma-related bone disease. Intravenous zoledronic acid or pamidronate are the recommended bisphosphonates can be used at the Investigator's discretion. Nonsteroidal anti-inflammatory drugs (NSAIDs, including aspirin/acetysalicylic acid) use is not prohibited; although their use is generally discouraged in the setting of active renal disease.

6.5.3 Prohibited Medicines

Additional dexamethasone with the intention to treat the underlying disease.

Strong CYP3A inhibitors/inducers must stop at least 7 days before the first administration of the study intervention and during the study intervention administration (i.e., clarithromycin, itraconazole, ketoconazole, nefazodone, neflifavir, ritonavir boceprevir, cobicistat, conivaptan, danoprevir and ritonavir, elvitegravir and ritonavir, indinavir and ritonavir, lopinavir and ritonavir, paritaprevir and ritonavir and (ombitasvir and/or dasabuvir), posaconazole, ritonavir, saquinavir and ritonavir, telaprevir, tipranavir and ritonavir, troleandomycin, voriconazole, diltiazem, idelalisib, as well as carbamazepine, enzalutamide, mitotane, phenytoin, rifampin. For further details and update refer to the Food and Drug Administration Drug Development and Drug Interactions website and the Drug Interactions Table™ website.

All herbal supplements known to inhibit or induce CYP3A are prohibited. Participants will be instructed to avoid any intake of grapefruit, grapefruit juice, Seville oranges, Seville orange marmalade, or other products containing grapefruit or Seville oranges, St. John's wort as well as any other CYP3A inhibiting or inducing herbal supplements starting at least 7 days before the first administration of the study intervention and during the study intervention administration.

Any P-gp inhibitors (including herbal supplements) must stop at least 7 days before the first administration of the study intervention and during the study intervention administration (i.e., amiodarone, carvedilol, clarithromycin, dronedarone, itraconazole, lapatinib, lopinavir and ritonavir, propafenone, quinidine, ranolazine, ritonavir, saquinavir and ritonavir, telaprevir, tipranavir and ritonavir, verapamil). For further details and update refer to the Food and Drug Administration Drug Development and Drug Interactions website and the Drug Interactions Table™ website.

Medications known to prolong the QT/QTc interval must stop at least 7 days before the first administration of the study intervention and are not allowed during the study intervention administration. A list of medication is attached in the [Appendix 4](#), for further details and update refer to website at www.crediblemeds.org.

6.5.4 Other Interventions

Not applicable.

6.6 Dose Selection and Modification

Dose escalation will proceed according to the SMC recommendation until the 50 mg dose level or the MTD is reached (whichever is lower). For further dose cohorts, a SMC will meet and review all available data to provide recommendations on the next dose level. In case escalation should proceed to doses higher than 50 mg, a protocol amendment will be submitted. Details are described in the SMC charter. The SMC receives outputs of a Bayesian dose-toxicity model estimated DLT probabilities for potential next dose levels. The Bayesian model will be based on prior, observed number of evaluable participants and number of participants with DLT. Further details on the Bayesian model are provided in Section 9.4.2. Further details on the SMC are provided in Section 10.

A DLT is defined as any of the AEs listed below as assessed by the Investigator and/or the Sponsor at any dose and regimen, and judged not to be related to the underlying disease or any previous or concomitant medication or concurrent condition occurring during the DLT observation period (first treatment cycle), according to the NCI-CTCAE v 5.0. Any DLT must be confirmed by the SMC.

During the DLT assessment period: Treatment with transfusions or growth factors (e.g., G-CSF, erythropoietin) is not permitted. Transfusions are only permitted if clearly related to multiple myeloma.

Participants who develop a DLT will permanently discontinue treatment.

Participants who did not receive $\geq 80\%$ of the planned cumulative dose or missed more than 20% of doses in the DLT period will not be considered in the DLT analysis set unless they experienced a DLT.

AEs judged as DLT will include:

- Any Grade ≥ 3 nonhematologic AE with exception of:
 - Single laboratory values out of abnormal range that have no clinical correlate, and resolve to Grade ≤ 1 or to Baseline within 7 days with adequate medical management
 - Grade 3 diarrhea persisting ≤ 72 hours after initiation of medical management
 - Nausea and vomiting of ≤ 72 h duration with adequate and optimal therapy
 - Transient (< 1 week) Grade 3 fatigue, local reactions, flu-like symptoms, fever, and headache (≤ 72 h) that resolves to Grade ≤ 1 with adequate treatment
 - Grade 3 nonrecurrent skin toxicity that resolves to Grade ≤ 1 in less than 7 days after initiation of medical management
 - Asymptomatic Grade ≥ 3 lipase or amylase elevation not associated with clinical manifestations of pancreatitis.
- Hy's law: Evidence of hepatocellular toxicity without clear alternative reason to explain the observed liver-related laboratory abnormalities, such as increase in AST or ALT of ≥ 3 x

ULN elevation and elevation of serum total bilirubin $\geq 2 \times$ ULN, without initial findings of cholestasis (elevated serum ALP) or other apparent clinical causality (eg viral hepatitis A, B, C or co-medication)

- Any death not clearly due to the underlying disease or extraneous causes
- Any Grade ≥ 4 hematologic AE, and:
 - Grade ≥ 3 febrile neutropenia with ANC $<1000/\text{mm}^3$ and a single temperature of $>38.3^\circ\text{C}$ (101°F) or a sustained temperature of $\geq 38^\circ\text{C}$ (100.4°F) for more than 1 h
 - Grade ≥ 3 thrombocytopenia with medically concerning bleeding
 - Grade 4 thrombocytopenia lasting >7 days, or platelets $<10,000/\text{mm}^3$ at any time

Except:

- Isolated Grade 4 lymphopenia without clinical correlate
- Any Grade 4 neutropenia of < 7 days duration not associated with any clinical symptoms.

- Neuropathic Pain or Peripheral Sensory or Motor Neuropathy:
 - Any aggravation by 2 grades or any Grade ≥ 3 (severe symptoms: limiting self-care Activity of Daily Life [ADL]).
- Any TEAE the SMC deems clinically relevant, that impairs daily function or abnormality occurring in participants treated with M3258 -/+ combination with dexamethasone at any time in Cycle 1 and any toxicity at any time in Cycle 1
- A study intervention-related TEAE (observed in subsequent cycles) that in the opinion of the SMC is of potential clinical significance such that further dose escalation would expose participants to unacceptable risk.

Any DLT will be confirmed by the SMC.

Table 11 describes the recommended individual dose modifications related to M3258-related neuropathic pain or peripheral sensory or motor neuropathy when experienced by participants outside of DLT period. **Table 12** describes the individual dose modifications and temporary or permanent treatment discontinuations for M3258-related hematologic toxicities when experienced by participants outside of DLT period. **Table 13** describes the individual recommended temporary treatment discontinuations for M3258-related general toxicities when experienced by participants outside of DLT period.

Table 11 Recommended Dose Modification for New Onset or Worsening Neuropathic Pain and/or Peripheral Sensory or Motor Neuropathy (outside of DLT Period)

Severity of Peripheral Neuropathy Signs and Symptoms ^a	Modification of Dose and Regimen
Grade 1 (asymptomatic: loss of deep tendon reflexes or paresthesia) without pain or loss of function	No action
Grade 1 with pain or Grade 2 (moderate symptoms: limiting instrumental ADL ^b)	Reduce M3258 dose by one dose level (based on dose escalation part) or at least by 50% if no lower dose level is available
Grade 2 with pain or Grade 3 (severe symptoms: limiting self-care ADL ^c)	Withhold M3258 therapy until toxicity resolves to Baseline or Grade 1 without pain, then reinitiate with a reduced dose of M3258 by one dose level (based on dose escalation part) or at least by 50% if no lower dose level is available If recurrence to Grade 2 with pain or higher, permanently discontinue M3258.
Grade 4 (life-threatening consequences: urgent intervention indicated)	Permanently discontinue M3258.

ADL = Activities of daily living; DLT = Dose-limiting toxicity; NCI = National Cancer Institute.

a Grading based on NCI Common Terminology Criteria for Adverse Events (CTCAE) v5.0.

b Instrumental ADL: refers to preparing meals, shopping for groceries or clothes, using telephone, managing money etc.

c Self-care ADL: refers to bathing, dressing and undressing, feeding self, using the toilet, taking medications, and not bedridden.

Table 12 Dose Modifications and Temporary/Permanent Treatment Discontinuation for Hematologic Toxicity (outside of DLT Period)

Hematologic Toxicity	Dose Modification
Neutropenia Grade 3 (without complications)	No dose reduction, consider treatment with G-CSF
Grade 3 Neutropenia associated with fever ($\geq 38.5^{\circ}\text{C}$) or neutropenia Grade 4	Hold M3258 until recovery to Baseline OR \leq Grade 2. Upon recovery, restart M3258 at current dose and consider G-CSF support. If recurrence is seen, reduce M3258 by one dose level (based on dose escalation part) or at least by 50% if no lower dose level is available. If second occurrence, permanently discontinue dosing
Thrombocytopenia Grade 3 (without complications)	No dose reduction required
Platelet count $< 25,000 / \mu\text{L}$ (i.e., Grade 4) or Grade 3 thrombocytopenia with bleeding	Hold M3258 until recovery to Baseline Or \leq Grade 2. Upon recovery, restart at a dose which is one dose level lower (based on dose escalation part) or at least by 50% if no lower dose level is available.

DLT = Dose limiting toxicity; G-CSF = granulocyte-colony stimulating factor.

Table 13 Recommended Temporary Treatment Discontinuation for General Toxicity (outside of DLT Period)

Organ involved	Specifics	Toxicity NCI-CTCAE 5.0 Grade	Management of Toxicity with permanent Discontinuation or Dose Interruption and Modification
Renal	Creatinine increased	Grade 3	Hold the M3258 until recovery to Grade ≤ 1 or Baseline. Upon recovery or returning to baseline, dosing may continue at same or lower level based on clinical judgment.
Hepatic	Increased AST /ALT	Grade 3	Isolated occurrence; repeat test within 72 hours; persistent or worsening, may hold off the M3258 until recovery to Grade ≤ 1 or Baseline, based on Investigator's clinical judgement.
	Increased total bilirubin	Grade 2+	Isolated occurrence; repeat test within 72 hours; persistent or worsening, may hold off the M3258 until recovery to Grade ≤ 1 or Baseline, based on Investigator's clinical judgement.
Other nonhematological toxicities	i.e., diarrhea, vomiting; GI hemorrhage	Grade 2+	Withhold M3258 administration until recovery to Grade ≤ 1; or to Baseline. symptomatic treatment in accordance to standard medical practice
Other	Grade 3+	Hold M3258 based on Investigator's clinical judgement.	

ALT = Alanine aminotransferase; AST = Aspartate aminotransferase; DLT = Dose-limiting toxicity; G-CSF = granulocyte-colony stimulating factor; GI = Gastrointestinal.

Dose reduction of M3258 for safety and tolerability reasons by one dose level (based on dose escalation part) or at least by 50% if no lower dose level is available or decided by SMC is permitted for individual study participant at any time during the study intervention, except for participants in the first cohort. M3258 dose escalation should not be considered for an individual participant once dose modification has been applied for safety or tolerability reasons.

If M3258 dosing were withheld for more than 2 weeks for scheduled dose for any reason, participant should discontinue the study intervention permanently. The study participant should complete End-of-Treatment visit and then should complete the reminder of the study period as Follow-Up period per the SoA ([Table 1](#) and [Table 2](#) for Part A; [Table 3](#) and [Table 4](#) for Part B).

Dose modification or deferral should always be discussed with the Sponsor Medical Responsible.

Dexamethasone

Dexamethasone may be dose reduced according to [Table 14A](#) and [Table 14B](#) or institutional guidelines, if applicable, for toxicities assessed as strictly related to dexamethasone. In those cases, where the toxicity cannot be attributed to dexamethasone, the dose of M3258 should be reduced first (see Section [6.9.1](#)).

Dose modification or deferral should always be discussed with the Sponsor Medical Responsible.

Organ involved	Specifics	Toxicity NCI-CTCAE v5.0 Grade	Management of Toxicity with permanent Discontinuation or Dose Interruption and Modification
Acute pancreatitis			Permanently discontinue dexamethasone.
Gastrointestinal	Dyspepsia, gastric, or duodenal ulcer,		Institute proton pump inhibitor.
	Gastritis (requiring medical management)	Grade 1-2	If symptoms persist or worsen despite measures, reduce dexamethasone by 50% (eg., 20 mg per week to 10 mg per week).
	Requiring hospitalization or surgery	Grade \geq 3	Hold dexamethasone until symptoms adequately controlled. Restart and reduce dexamethasone by 50% from initial dose along with the use of proton pump inhibitors.
Metabolic	Hyperglycemia	Grade \geq 2	Diet control and monitor closely.
		Grade \geq 3	Treat with insulin or oral hypoglycemics as needed.
			If uncontrolled despite these measures, reduce dexamethasone by 50% from initial dose.
Cardiovascular	Edema (limiting function and unresponsive to therapy or anasarca)	Grade \geq 2	Diuretics as needed and dose reduction by 50% should be considered. If edema persists despite these measures, consider reducing dexamethasone dose from 10 mg to 5 mg.
			Monitor closely (weekly weight, restrict hydration).
Musculoskeletal	Muscle weakness (interfering with function and/or interfering with activities of daily living)	Grade \geq 2	Reduce dexamethasone by 50%.
			In case of no improvement or worsening, further (50%) dose reduction is recommended. If weakness persists despite these measures, permanently discontinue dexamethasone.
Neurological	Confusion or mood alteration	Grade \geq 2	Hold dexamethasone until symptoms resolve. Restart and reduce dexamethasone by 50%. Upon worsening or no improvement, consider further reduction of dose to 5 mg. Permanently discontinue dexamethasone if symptoms recur.
Constitutional	Insomnia	Grade \geq 2	Advise dexamethasone administration in the morning only.
			If symptoms persist, reduce the dose by 50% (eg., 20 mg to 10 mg to 5 mg).

Modified from Palumbo and Gay, 2009

Table 14B Recommended Dose Reduction for Dexamethasone

First Dose Reduction	Second Dose Reduction	Third Dose Reduction
Reduce dexamethasone by 50% from starting dose	Give dexamethasone only on Day 8, 15, 21	Discontinue dexamethasone

Refer to [Palumbo and Gay, 2009](#).

Part B

In the expansion cohorts, the SMC will also monitor the safety of the participants treated with M3258 at RDE in combination with 20 mg/day dexamethasone and will meet after 3, 6, and subsequently every 6 participants have finished the DLT period or discontinued, unless a change in dosing has occurred. In case dosing in the expansion cohort was changed, the next SMC will be held after 3 participants have finished the DLT period or discontinued. Thereafter the SMC will evaluate the safety after every 6 participants (see Section 10). The SMC can recommend continuing enrollment at the RDE, changing the dose, or stopping the expansion part of the study. The SMC decisions in the expansion phase will also be supported by Bayesian modeling. Study Intervention after the End of Study.

The Sponsor will not provide any additional care to participants after they leave the study because such care would not differ from what is normally expected for participants with MM.

Part A and B

If a participant receives M3258 QD and misses taking a scheduled dose of M3258, then within a window of 12 hours it is acceptable to replace the missed dose. If in the QD dosing regimen the window is more than 12 hours after the scheduled dose time, then the missed dose should not be taken, and participants should be instructed to take the next scheduled dose.

If a participant receives M3258 twice-per-week and misses taking a scheduled dose within a window of 24 hours, then it is acceptable to replace the missed dose. For the twice-per-week dosing regimens in case of a delay of the scheduled dose, the missed dose should be taken as soon as possible, but at least two days (minimum 36 h) before the next scheduled dose.

If a participant vomits after taking M3258, the participant should not repeat the dose, but resume dosing at the time of the next scheduled dose.

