Treatment cycles with M3258 -/+ combination with dexamethasone will be repeated every 21 or 28 days; hence, for a cycle of treatment to begin, the participant's blood ANC must be \geq 1,000 mm³ and the platelet count must be \geq 75,000 mm³. Additionally, all other toxicities considered to be related to study intervention must have resolved to \leq Grade 1 or to the participant's Baseline value.

If the participant fails to meet the above-cited criteria for treatment, re-initiation of the next cycle of treatment should be delayed for one week. At the end of which, the participant should be re-evaluated to determine whether the criteria for re-treatment have been met. If a delay in the initiation of the next cycle of more than two weeks is required because of incomplete recovery from toxicity, then this event should be considered a DLT. If toxicity does not resolve by two weeks, then the participant should be discontinued from the study. This decision will be made in the context of emerging clinical data and in consultation with Sponsor Medical Responsible. If, in the opinion of the Investigator and the Sponsor Medical Responsible, it is in the participant's best interest to continue the treatment with M3258 -/+ combination with dexamethasone, the study intervention will only be resumed after recovery from toxicity to \leq Grade 1 or Baseline values. Additionally, the dose of study intervention should be reduced by at least 1 dose levels. If the DLT recurs upon resuming study intervention at a lower dose, the study intervention should immediately be discontinued. For the first study cohort, no dose reduction will be allowed.

7

Discontinuation of Study Intervention and Participant Discontinuation/Withdrawal

7.1

Discontinuation of Study Intervention

Stopping Rules for Individual Participants:

The Investigator must consider discontinuation of study intervention for abnormal liver function when a participant meets one of the conditions outlined in Section 6.6 or if the Investigator believes that it is in best interest of the participant.

All events of ALT \geq 3 \times ULN and bilirubin \geq 2 \times ULN ($> 35\%$ direct bilirubin) or ALT $>$ 3 \times ULN and international normalized ratio (INR) $>$ 1.5, if INR measured, may indicate potential severe liver injury (possible Hy's Law) and must be reported as an AE and SAE.

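### For a next-cycle delay of more than two weeks, which Protocol 6.9.1 calls a DLT, Section 6.6 requires permanent discontinuation while 6.9.1 allows conditional resumption at a lower dose

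*Protocol*

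**What the plan says.** Two statements in Protocol Section 6.6 bear on the point. The first is in the DLT definition: "Participants who develop a DLT will permanently discontinue treatment". It carries no exception and no cross-reference. The second follows Table 13: a participant whose scheduled M3258 has been withheld for more than two weeks, for whatever reason, should stop study intervention permanently.

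Section 6.9.1 sets the conditions for starting a new cycle. If the start has to be put off by more than two weeks "because of incomplete recovery from toxicity, then this event should be considered a DLT". The next sentence gives the default: "If toxicity does not resolve by two weeks, then the participant should be discontinued from the study". The paragraph then opens a second route. If the Investigator and the Sponsor Medical Responsible consider that "it is in the participant's best interest to continue the treatment with M3258", with or without dexamethasone, then "the study intervention will only be resumed after recovery from toxicity" to Grade 1 or less or to Baseline. "Additionally, the dose of study intervention should be reduced by at least 1 dose levels". It closes with "If the DLT recurs upon resuming study intervention at a lower dose, the study intervention should immediately be discontinued" and "For the first study cohort, no dose reduction will be allowed".

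The list of reasons for discontinuing study intervention in Section 7.1 does not mention a DLT.

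**The concern.** The sentence about a DLT recurring after resumption has meaning only if someone with a DLT has gone back on treatment. Under the DLT sentence in 6.6 no such participant can exist. So two participants with the same delay could be handled in opposite ways, each in line with some part of the protocol.

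This is a first-in-human trial, and what is at stake first is dosing after an event the protocol itself calls dose-limiting. Reported results also depend on the choice. The on-treatment period runs to 30 days after the end of study intervention (SAP 9.4), so resuming lengthens the window for treatment-emergent events. Events leading to permanent discontinuation (SAP 15.2.1), exposure duration (SAP 13) and the duration-of-treatment plot (SAP 14.2) move with it.

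**Working it through.** No design figure is involved, so the check is textual. Take one participant whose next cycle is delayed by more than two weeks because a toxicity has not recovered.

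| Place | Does it apply? | Instruction |
|---|---|---|
| 6.6, DLT definition | Yes, because 6.9.1 classes the event as a DLT | Stop permanently |
| 6.6, after Table 13 | Yes, because scheduled doses have been withheld for more than two weeks | Stop permanently |
| 6.9.1, default | Yes | Discontinue |
| 6.9.1, second route | Yes, if both parties agree and recovery occurs | Resume at least one dose level lower |
| 7.1, list | DLT not listed | Does not settle it |

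1. Rows 1 and 2 each exclude row 4. Row 3 does too, but row 4 is written as a qualification of it within the same paragraph.
2. No statement gives either section precedence.
3. The rules do not separate by time. The 6.9.1 paragraph governs the start of any next cycle, including Cycle 2 after Cycle 1 toxicity. The DLT list in 6.6 also admits some later-cycle events on the SMC's judgement.
4. The rules do not separate by study part. The 6.9.1 paragraph covers M3258 with or without dexamethasone and refers to the first cohort.
5. Tables 11 to 13 apply outside the DLT period and are not needed for the conflict.

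Effect on the DLT analysis: a participant with a DLT in the DLT period enters the DLT set whatever number of doses was given (Protocol 9.3, SAP 8.1) and is analysed at the planned dose when less than planned was received (SAP 9). Stopping or resuming afterwards leaves that count unchanged.

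Size: the only figures available concern DLTs of every kind. Using the prior DLT probabilities in Protocol 9.4.2 and the 3, 3, 6, 6 scenario in 9.2, and assuming that the cohorts of six are at 35 and 50 mg:

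- Prior means: 3 × 0.15 + 3 × 0.19 + 6 × 0.24 + 6 × 0.28 = 4.14.
- Prior medians: 3 × 0.08 + 3 × 0.13 + 6 × 0.18 + 6 × 0.22 = 3.03.

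Neither figure isolates cycle-delay DLTs, and the documents give no rate for them.

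**The case against.** The best defence is that 6.9.1 is a specific rule for a specific event. A delayed cycle start is not on the 6.6 list of DLTs; 6.9.1 adds it and writes its own procedure. Its default is to stop, and resumption needs joint agreement, recovery and a dose reduction. Reduction is ruled out in the first cohort, which appears to close the route there. The two-week rule in 6.6 also says should rather than will, and the protocol asks that dose modification or deferral be discussed with the Sponsor Medical Responsible.

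Much of this stands as a limit on scope. A reader might infer that anyone with a DLT may resume. The documents do not support that, because nothing in 6.9.1 reopens treatment after an ordinary DLT on the 6.6 list. A reader might also infer that a site may continue on its own decision, and it may not.

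The defence does not remove the conflict. Neither section says that 6.9.1 is an exception. Even if it were read as one to the DLT sentence, the two-week rule in 6.6 meets the same length of interruption and covers any reason.

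Three further inferences about the analysis also go too far:

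- **Response evaluability.** SAP 14.1 counts as non-responders those participants with at least one on-treatment assessment who withdraw before a confirmed response. Response status could differ between the two routes; evaluability mostly would not.
- **Visibility of dosing after a DLT.** The DLT listing gives dates and action taken (SAP 15.1), and another listing gives every administration with date and dose (SAP 13). Such dosing can already be seen.
- **Number affected.** Multiplying the 25% target by 18 planned participants gives 4.5. But 25% is the target at the MTD, not an expected rate over all cohorts, and the product counts every DLT.

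**Conclusion.** The inconsistency is real and confined to the cycle-delay DLT. For that participant both statements in 6.6 require permanent discontinuation, while 6.9.1 permits conditional resumption. The consequences are for exposure after the event, the treatment-emergent window, discontinuation counts and treatment duration.

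A reader might go on to infer that the dose-finding result is at risk. The documents do not support this: the DLT count in the Bayesian model is the same under either rule for a DLT in the DLT period. Whether a delay declared after Cycle 1 counts towards the model is a matter of DLT definition, and stopping or resuming does not alter it.

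The number of participants affected cannot be estimated. SAP Section 7 also records that the study stopped before Part B began and before Part A met its primary objective, so the planned 18 is not the working denominator. The conclusion rests on reading the 6.9.1 paragraph as applying to both parts and to every cycle start, as its wording indicates.

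**What to change.** Reconcile four places in the protocol: the DLT discontinuation sentence in 6.6, the two-week withholding rule in 6.6, the cycle-start paragraph in 6.9.1 and the discontinuation list in 7.1. Either one rule should apply to the cycle-delay DLT, or the text should state which DLTs each rule covers and which section prevails. The sponsor and investigators must decide which rule is clinically right; no view is taken here.

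The cost is protocol wording only. No analysis, sample size or SAP output needs to change. Because the study has stopped, the clarification now mainly helps readers of the study report interpret treatment duration and discontinuations for any participant to whom the paragraph applied.
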